|   | 
lack of existing evidence-based data for any treatment in alopecia areata, there is a strong rationale for testing CTLA4-Ig treatment in this disease.
  |
| 
Study Objectives:
 Primary:
 Secondary:
             | 
The study's primary efficacy endpoint will be the proportion of responders after 6 months of treatment, with response defined as 50% or greater hair re-growth from baseline as assessed by SALT score at week 24. This is a relatively strict definition for defining responders and non-responders and was chosen to minimize the potential for spontaneous remission, in which fewer than 10% are expected to achieve this magnitude of hair regrowth spontaneously.
 
As secondary endpoints, efficacy will be measured by changes in hair re-growth as a continuous variable as determined by physical exam and Canfield photography, as well as patient and physician global evaluation scores. To assess the durability of responses, patients will continue to be followed for an additional 6 months off treatment or until it is determined that relapse has occurred. Additionally, patient reported outcomes, safety measures, incidence and timing of relapse will be important secondary outcomes. We will also explore the efficacy of treating 2 patients with current alopecia totalis or universalis, and in doing so, will compare, on an exploratory basis, the rate of occurrence of hair regrowth in patients with moderate to severe patch type alopecia areata compared to those with current alopecia totalis or universalis.
 
In addition, response to abatacept treatment will be examined on an exploratory basis for correlation with the presence or absence of the AA GWAS risk haplotype.
 |
| 
Study Design:
   | 
Open label pilot study of 6 months of abatacept 125mg SC per week in the treatment of moderate to severe AA and current alopecia totalis or universalis, followed by 6 months follow-up off drug to assess the incidence and timing of recurrence of disease. Treatment may be extended by up to 6 additional months beyond the initially planned 6 months of treatment if clinically indicated at the discretion of the investigator.
  |

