| 
Statistics:
 | 
This is a small exploratory open label pilot study to identify an efficacy signal in alopecia areata.
 
Based on two recently completed randomized trials (Strober et al, 2008; Price et al, 2009) in similar patient populations (moderate to severe AA) we expect placebo response rates to be between 6% (>50% improvement in SALT score (Olsen et al, 1999)) and 12% (>25% improvement). We have chosen our primary endpoint conservatively (proportion of patients with >50% improvement in SALT index) as a relatively strict criteria that should minimize placebo response rates to 10% or less (0-2 of 15 subjects). This allows a higher degree of confidence that appreciable response rates are attributable to drug rather than spontaneous remission.
 
Power analysis. Assuming a historically known placebo response rate of 10% and the usual 5% level of significance (alpha), the sample size of 15 would provide 80.7% power to detect a difference of 30% in the response rate between the experimental treatment group and the historical placebo group.
 
Since this is a small open label proof of concept study, we recognize that it will likely lack adequate power to conclusively demonstrate small efficacy signals (particularly if the assumed detectable difference of 30% is not met). Yet, descriptive summaries of all the primary and secondary efficacy outcomes (proportions for binary outcomes, means for continuous outcomes) will provide a preliminary indication of the effect size (even if smaller than 30%) that will aid design of subsequent efficacy trials.
 
Differences in the incidence of regrowth between patients with patch type AA vs patients with alopecia totalis or universalis will also be analyzed on an exploratory basis. In addition, response to abatacept treatment will be examined on an exploratory basis for correlation with the presence or absence of the AA GWAS risk haplotype.
 
To assess safety as a secondary endpoint, we will summarize via descriptive statistics, the occurrence of adverse events for the study group.
 
Accrual projections. The Dermatology clinic and private practice at CUMC currently sees 600 AA patients yearly, of which we anticipate 20-30% would be eligible (>40% hair loss). Accrual will be greatly facilitated by targeted recruitment through our existing NAAF registry which includes 400 AA patients in the New York area, the majority of which have patchy type disease. Thus, complete accrual of 15 subjects should be feasible within 1 year from a pool of >100 eligible subjects yearly.
 |

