## **2 STUDY OBJECTIVES**

### **2.1 Primary Objective**

The study’s *primary efficacy endpoint* will be the proportion of responders after 6 months of treatment, with response defined as 50% or greater hair re-growth from baseline as assessed by SALT score (Olsen et al, 1999) at week 24. This is a relatively strict definition for defining responders and non-responders and was chosen to minimize the potential for spontaneous remission, in which fewer than 10% are expected to achieve this magnitude of hair regrowth spontaneously. To assess the durability of responses, patients who achieve 50% regrowth from baseline during the first 6 months, will continue to be followed for an additional 6 months off treatment or until it is determined that relapse has occurred

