### **Week 25 to 48 (follow-up period off study medication)**

All patients will be seen at week 36 and 48, after completion of 6 months of study drug, to determine durability of response or evidence for a delayed effect. Importantly patients who achieved  $\geq$  50% regrowth as measured by SALT score (responders) will be seen at week 36,

and 48 after end of study treatment in order to assess the frequency and timing of relapse or to capture the occurrence of further regrowth.

Relapse will be defined as any recurrence of hair loss in responders (subjects achieving greater than 50% decrease in SALT score from baseline during the first 6 months of the study) who had achieved stable regrowth without continued loss for at least 2 months; and loss of  $\geq$  25% of regrowth in patients who had achieved 50% regrowth during treatment but still had chronic low grade hair loss.

Nonresponders will also continue follow-up in order to assess for delayed response.

Efficacy evaluations: SALT, PGA, Patient global assessment and patient quality of life assessment will be performed at Weeks 36, and 48.

Blood draws for safety parameters will be conducted at week 30 if deemed necessary to assess normalization of any previously abnormal values.

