## **7 STATISTICAL CONSIDERATIONS**

### **7.1 Sample Size Determination**

Based on two recently completed randomized trials (Price et al, 2008; Strober et al, 2009) in similar patient populations (moderate to severe AA) we expect placebo response rates to be between 6% (>50% improvement in SALT score) and 12% (>25% improvement). We have chosen our primary endpoint conservatively (proportion of patients with >50% improvement in SALT index) as a relatively strict criteria that should minimize spontaneous remission rates to 10% or less (0-2 of 15 subjects). This allows a higher degree of confidence that appreciable response rates are attributable to drug rather than spontaneous remission.

Assuming a historically known placebo response rate of 10% and the usual 5% level of significance (alpha), the sample size of 15 would provide 80.7% power to detect a difference of 30% in the response rate between the experimental treatment group and the historical placebo group.

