### **7.3 Endpoint Definitions**

1. Proportion of patients with >50% improvement in SALT index at 24 weeks

2. Percent hair regrowth from baseline determined by SALT measurements following 12, 24 weeks of treatment and at weeks 36 and 48 following discontinuation of treatment.
3. Comparison of the proportion of responders in the experimental group with the historically known placebo response rate (<10%), with response defined as 50% change in SALT score (50% regrowth) from baseline, at weeks 12, 36 and 48.
4. Comparison of the proportion of subjects in the experimental group and the proportion of subjects in the historical control group attaining global overall improvement SALT score of A5 (100% coverage) supported by  $\leq$  SALT 25 at weeks 12, 24, 36 and 48.
5. Change in PGA (Physician Global Assessment) based on evaluation of live evaluations and standardized photographs between baseline, week 12, 24, 36 and 48.
6. Change in patient global assessment between baseline, weeks 12, 24, 36, and 48.
7. Change in patient quality of life assessment from baseline to weeks 12, 24, 36, and 48.
8. Frequency of occurrence and timing of relapse (as defined above) in responders followed for 6 months off therapy.
9. To assess safety, we will summarize the incidence of adverse events for the study group.

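### The 80.7% power for 15 subjects names no test and is a figure no count of responders can deliver (exact: 78.3% at 5/15); separately, the responder cut-point is at least 50% in some sections and above 50% in others.

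*Combined protocol and SAP*

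**What the plan says.** **Power.** Section 7.1, repeated in the Synopsis statistics, takes a historical placebo rate of 10% and a 5% significance level, and states that "the sample size of 15 would provide 80.7% power to detect a difference of 30% in the response rate". The implied alternative is 10% + 30% = 40%. No test, sidedness or critical value is given. Section 7.4.3 plans descriptive summaries (proportions and means) and names no interval.

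**Benchmark.** The Synopsis says the strict endpoint "should minimize placebo response rates to 10% or less (0-2 of 15 subjects"); section 7.1 says it "should minimize spontaneous remission rates to 10% or less (0-2 of 15 subjects").

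**Cut-point.**

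| Place | Response |
|---|---|
| Synopsis objectives | "with response defined as 50% or greater hair re-growth from baseline as assessed by SALT score at week 24" |
| 2.1, and the same wording in 6.4.1 | "with response defined as 50% or greater hair re-growth from baseline as assessed by SALT score" |
| 7.1, and the same wording in the Synopsis statistics | "proportion of patients with >50% improvement in SALT index" |
| 7.3 item 1 | "Proportion of patients with >50% improvement in SALT index at 24 weeks" |

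In section 4.1 (weeks 25 to 48), an at-least sign stands before "50% regrowth as measured by SALT score (responders) will be seen at week 36". The relapse definition that follows, repeated in 6.4.2, describes responders as those with a SALT decrease greater than 50%.

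**The concern.** With 15 subjects, any test against a fixed 10% comes down to a count: at least k responders. Power then moves in large steps, and a value such as 80.7% may belong to no usable rule. Without a named test, the reader cannot tell which count the power refers to.

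No pass/fail decision hangs on this. What is at stake is how the week-24 proportion will be read. Sections 2.2 (item 2), 6.4.2 (item 2) and 7.3 (item 3) all list a comparison of the responder proportion with the historical rate, and 2.2 includes week 24. None gives a method. A result of 3/15 or 4/15 would exceed the quoted range of 0 to 2, yet the plan offers nothing to show how much that means.

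The cut-point bears on the same count: a subject at exactly 50% regrowth is a responder under 2.1 and not under 7.3 item 1.

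**Working it through.** **Inputs.** n = 15, p0 = 0.10, alpha = 0.05, stated power 80.7% (7.1 and Synopsis); p1 = 0.10 + 0.30 = 0.40.

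**1. The plan's own figure.** Two-sided 5% approximations, one sample against a fixed rate:

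- Arcsine: h = 2·asin(√0.40) − 2·asin(√0.10) = 1.3694 − 0.6435 = 0.7259. Power = Φ(h√15 − 1.960) = Φ(2.812 − 1.960) = Φ(0.852) = **80.3%**.
- Score with continuity correction: standard errors √(0.09/15) = 0.0775 under 10% and √(0.24/15) = 0.1265 under 40%. Power = Φ[(0.30 − 1/30 − 1.960 × 0.0775)/0.1265] = Φ(0.908) = **81.8%**.

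The stated 80.7% lies between them. No variant tried gives exactly 80.7%.

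**2. Exact binomial.** P(X ≥ k), X ~ Bin(15, p):

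| Rule | Type I error (p = 0.10) | Power (p = 0.40) |
|---|---|---|
| ≥ 3/15 | 18.4% | 97.3% |
| ≥ 4/15 | 5.6% | 90.9% |
| ≥ 5/15 | 1.3% | 78.3% |
| ≥ 6/15 | 0.2% | 59.7% |

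The smallest count that holds 5% is 5/15. It is the same at one-sided 5% and one-sided 2.5%, because 4/15 has a tail of 5.6% and 5/15 a tail of 1.3%. Power goes from 90.9% to 78.3% with nothing between. Difference from the stated figure: 80.7 − 78.3 = **2.4 points**.

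**3. Reading the count.** Clopper-Pearson 95% intervals:

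- 3/15: 4.3% to 48.1%
- 4/15: 7.8% to 55.1%
- 5/15: 11.8% to 61.6%

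Of these, only 5/15 excludes 10%. If the true rate is 10%, three or more responders still occur 18.4% of the time.

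**4. The assumption of one common rate.** The 78.3% needs a 40% rate in every subject. Two to five subjects may have current alopecia totalis or universalis (4.2.1 item 6), and section 1.5 expected a lower response in such patients. The documents give no rate for them, so as an illustration take 40% in patch-type disease and a range from 0% upward in these subjects. P(at least 5 of 15), from the sum of two binomials:

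| Assumed rate in AT/AU | Two such subjects | Five such subjects |
|---|---|---|
| 40% | 78.3% | 78.3% |
| 10% | 68.3% | 48.8% |
| 0% (all five responders must come from the other 13 or 10) | 64.7% | 36.7% |

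**5. Cut-point.** One subject is 1/15 = 6.7 points. A single subject at exactly 50% could move the count from 4/15 (tail 5.6%) to 5/15 (tail 1.3%).

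**The case against.** **The exact test is one choice among several.** At 4/15 the uncorrected score test gives z = (0.2667 − 0.10)/0.0775 = 2.15 (two-sided p = 0.03), and the Wilson 95% interval is 10.9% to 52.0%, which excludes 10%. This stands: the 78.3% and the 5/15 belong to the exact test. It does not rescue 80.7%, though. Rejecting at 4/15 has true type I error 5.6% and power 90.9%, whichever formula leads there.

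**The study is an exploratory pilot.** The Synopsis and 7.4.3 admit limited power for small effects and plan descriptive summaries. This stands and limits the weight of the point. It does not remove it, because the plan also lists comparisons with the historical rate and gives no method for them.

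**The range 0 to 2 of 15 is a gloss, not an efficacy threshold.** Fair. Moreover, the plan expects 6% for improvement above 50%, and at 6% three or more responders occur only 5.7% of the time. The 18.4% belongs to the 10% that the power statement assumes.

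**The cut-point matters only at exactly 50%.** True, and the documents do not say how often that would happen. A reader might also infer from 6.4.2 that such a subject is neither responder nor nonresponder, since relapse refers to more than 50% and nonresponse to failing to achieve 50%. The documents do not support that. Section 6.4.2 also says that patients who achieve 50% regrowth are followed for relapse, and 4.1 labels at least 50% as responders.

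**Conclusion.** The point holds in limited form. The 80.7% is credible as a large-sample approximation, but no count out of 15 delivers it, and no rule that holds 5% exactly reaches it. The exact figure is 78.3% at 5/15, which is 2.4 points lower, given a 10% reference rate, a 40% true rate in all 15 subjects, and all 15 counted. Power is lower still if subjects with current alopecia totalis or universalis respond less often.

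The two cut-points are a real inconsistency in the primary endpoint. It is confined to a value of exactly 50% and worth at most 6.7 points per subject affected.

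A reader might infer that the sample size rests on an arithmetic error or that 15 is the wrong number. Neither follows: standard approximations on the plan's own inputs bracket the figure, and a gap of 2.4 points does not undermine 15 subjects in a pilot.

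**What to change.** 1. **7.1 and Synopsis statistics.** Name the exact binomial test of the week-24 responder proportion against 10%: critical value 5/15, exact type I error 1.3%, power 78.3% if the true rate is 40%. State that this assumes 40% in all 15 subjects, including the two to five with current alopecia totalis or universalis, whose response was expected to be lower, and that power falls if they respond less often.
2. **7.4.3.** Report the week-24 responder proportion with a Clopper-Pearson 95% interval beside the descriptive summaries. Give 5/15 as a benchmark, not a pass/fail rule.
3. **Cut-point.** Use 50% or greater, as in the primary objective, for this trial's endpoint in the Synopsis statistics, 7.1, 7.3 item 1 and the responder wording of the relapse definition (4.1 and 6.4.2). Leave unchanged the above-50% wording in 7.1 and the Synopsis that describes the 6% placebo rate in the historical trials, since it reports what those trials measured.

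Cost: a few sentences, and a stated power 2.4 points lower, just under 80%. Sample size, design and data collection stay as they are.

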### **7.2 Populations for Analyses**

The Dermatology clinic and private practice at CUMC currently sees 600 AA patients yearly, of which we anticipate 20-30% would be eligible (>30% hair loss). Accrual will be greatly facilitated by targeted recruitment through our existing NAAF registry, which includes 400 AA patients in the New York area, the majority of which have patchy type disease. Thus, complete accrual of 15 subjects should be feasible within 1 year from a pool of >100 eligible subjects yearly.

### **7.3 Endpoint Definitions**

1. Proportion of patients with >50% improvement in SALT index at 24 weeks

2. Percent hair regrowth from baseline determined by SALT measurements following 12, 24 weeks of treatment and at weeks 36 and 48 following discontinuation of treatment.
3. Comparison of the proportion of responders in the experimental group with the historically known placebo response rate (<10%), with response defined as 50% change in SALT score (50% regrowth) from baseline, at weeks 12, 36 and 48.
4. Comparison of the proportion of subjects in the experimental group and the proportion of subjects in the historical control group attaining global overall improvement SALT score of A5 (100% coverage) supported by  $\leq$  SALT 25 at weeks 12, 24, 36 and 48.
5. Change in PGA (Physician Global Assessment) based on evaluation of live evaluations and standardized photographs between baseline, week 12, 24, 36 and 48.
6. Change in patient global assessment between baseline, weeks 12, 24, 36, and 48.
7. Change in patient quality of life assessment from baseline to weeks 12, 24, 36, and 48.
8. Frequency of occurrence and timing of relapse (as defined above) in responders followed for 6 months off therapy.
9. To assess safety, we will summarize the incidence of adverse events for the study group.

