**Week 25 up to 72 (for subjects receiving optional additional treatment extension)**

Patient receiving an optional additional treatment extension of up to 6 months, at the discretion of the investigator, will continue to be seen every 6 weeks after week 24 while on the study medication, then at 12 weeks and 24 weeks after completion of up to 12 months of study drug, to determine durability or response or evidence for a delayed effects.

Efficacy evaluations: SALT, PGA, Patient global assessment and patient quality of life assessment will continued to be performed at every visit during optional additional treatment extension.

Blood draws for safety parameters will be conducted at 12 weeks after completion of study drug if deemed necessary to assess normalization of any previously abnormal values.

Adverse events will be assessed at every visit.

Standardized photographs of the subject's scalp will be done at every scheduled visit and will be used to support determination of percent hair regrowth. Photography will be performed using a high-resolution digital camera with Intellistudio system from Canfield Scientific, Inc. Patients will be positioned using a laser guide, after which photographs of the entire scalp will be taken at standardized locations and at a fixed distance. Close-up photographs may also be taken using an epiluminescent attachment in order to assess for the presence of early regrowth.

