#### Week 24 (Day 168 $\pm$ 7) – End of Treatment

- Vital signs, body weight
- Physical and dermatological examination
- Adverse events reporting, concomitant medication review
- Photography
- Physician evaluation utilizing the PGA and SALT scale
- Patient global assessment and quality of life assessment
- Urine pregnancy testing for WOCBP
- Clinical laboratory evaluation
- Scalp biopsy (4mm punch biopsy)
- Blood collection for immunological studies

Weeks 36 and 48 (Days 252 and 336  $\pm$ 7 days) – Observational Period

- Vital signs, body weight
- Physical and dermatological examination (only week 48)
- Adverse events reporting, concomitant medication review
- Photography
- Physician evaluation utilizing the PGA and SALT scale
- Patient global assessment and quality of life assessment
- Optional Scalp biopsy (4mm punch biopsy) – at the discretion of the principal investigator and with the consent of the subject, based upon perceived utility in context of individual patient response to therapy and durability of that response.
- Optional Blood collection for immunological studies, at the discretion of the principal investigator and with the consent of the subject.

Weeks 30, 36, 42, 48 (Extension Option)

Visit days will have an acceptable window of  $\pm$ 7 days.

- Vital signs, body weight
- Adverse events reporting, concomitant medication review
- Photography
- Physician evaluation utilizing the PGA and SALT scale
- Patient global assessment and quality of life assessment
- Urine pregnancy testing for WOCBP
- Physical and dermatological examination (week 36)
- Clinical laboratory evaluation, if indicated (at 12 weeks after end of study treatment)
- Optional Scalp biopsy (4mm punch biopsy) – at the discretion of the investigator and with the consent of the subject, based upon perceived utility in context of individual patient response to therapy and durability of that response.
- Optional Blood collection for immunological studies in addition to weeks 4 and 12, at the discretion of the investigator and with the consent of the subject.

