### **6.1.2 Study Drug Discontinuation**

If study drug administration is discontinued, the reason for discontinuation will be recorded.

Table 3: Schedule of Assessments

| Visit   | Screening | PPD reading | Base-line      | Week 4 | Week 8           | Week 12 | Week 18          | Week 24/ET | Week 30, 36, 42, 48 (optional) | 12 Weeks after end tx | 24 Weeks after end tx |
|---|-----------|-------------|----------------|--------|------------------|---------|------------------|------------|--------------------------------|-----------------------|-----------------------|
| Day   | -28 to -1 |             | 0              | 28±1   | 56±1             | 84±1    | 126±1            | 168±7      |                                |                       |                       |
| Informed Consent  | X         |             |                |        |                  |         |                  |            |                                |                       |                       |
| Inclusion/Exclusion Criteria  | X         |             | X              |        |                  |         |                  |            |                                |                       |                       |
| Medical History   | X         |             |                |        |                  |         |                  |            |                                |                       |                       |
| Body Weight   | X         |             | X              | X      | X                | X       | X                | X          | X                              | X                     | X                     |
| Physical/Cutaneous Exam   | X         |             |                |        |                  | X       |                  | X          |                                |                       | X                     |
| Vital Signs   | X         |             | X              | X      | X                | X       | X                | X          | X                              | X                     | X                     |
| Concomitant Medications   | X         |             | X              | X      | X                | X       | X                | X          | X                              | X                     | X                     |

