| Urine pregnancy test  |           |             | X              | X      | X                | X       | X                | X          | X                              |                       |                       |
| Scalp Biopsy  |           |             | X              | X      | (X) c | X       | (X) c | X          | (X) c               | (X) c      | (X) c      |
| Phlebotomy for immunological studies  |           |             | X d | X      | (X) c | X       | (X) c | X          | (X) c               | (X) c      | (X) c      |
| Training/reinforcement of training for self-administered SQ injection
Patient observed self-administering study medication |           |             | X b | X      | X                | X       | X                | X          | X                              |                       |                       |
| Chest X ray-1 view  | X         |             |                |        |                  |         |                  |            |                                |                       |                       |

aClinical laboratory evaluation consists of CBC, BMP, hepatic panel, and urinalysis. Additional evaluations will only be performed if needed to verify normalization of previously abnormal lab values.

bBaseline dose will be subcutaneous administration of abatacept.

c Optional additional Scalp biopsies (4mm punch biopsy) may be performed at the discretion of the investigator and with the consent of the subject, based upon perceived utility in context of individual patient response to therapy and durability of that response. Optional Blood collection for immunological may be performed at the discretion of the investigator and with the consent of the subject.

d Includes testing for AA GWAS risk haplotype

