## **6.4 Efficacy Assessments**

### **6.4.1 Primary Efficacy Assessment**

The study's *primary efficacy endpoint* will be the proportion of responders after 6 months of treatment, with response defined as 50% or greater hair re-growth from baseline as assessed by SALT score (Figure 6) at week 24. Treatment may be extended by up to an additional 6 months beyond the initial 6 months of treatment if clinically indicated at the discretion of the investigator.

This is a relatively strict definition for defining responders and non-responders and was chosen to minimize the potential for spontaneous remission, in which fewer than 10% are expected to achieve this magnitude of hair regrowth spontaneously.

SALT – Severity of Alopecia Tool

A. The proportion of scalp involvement is determined by dividing the scalp into 4 quadrants and estimating the percentage of the scalp surface that all the alopecic areas would occupy if placed together. The following groups will be used:

S: Scalp hair loss

- |                              |                              |
|------------------------------|------------------------------|
| _____ S0 = No hair loss      | _____ S4 = 76%-99% hair loss |
| _____ S1 = <25% hair loss    | _____ a = 76%-95% hair loss  |
| _____ S2 = 26%-50% hair loss | _____ b = 96%-99% hair loss  |
| _____ S3 = 51%-75% hair loss | _____ S5 = 100% hair loss    |

Body hair loss

- B0 = No body hair loss  
 B1 = some body hair loss  
 B2 = total (100%) body hair loss

Nail involvement

- N0 = No nail involvement  
 N1 = some nail dystrophy  
 N1a = 20 nail dystrophy

[figure not shown]
Percentage change from baseline (% regrowth) =  

$$\frac{[(SALT\ BL - SALT\ F/U) / SALT\ BL] \times 100\%}{}$$
absolute change from baseline  

$$\frac{SALT\ BL - SALT\ F/U}{}$$
absolute change from BL

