#### Secondary efficacy outcomes in detail

1. Percent hair regrowth from baseline determined by SALT measurements following 12, 24 weeks of treatment and during the observational phase at weeks 36 and 48.
2. Comparison of the proportion of responders in the experimental group with the historically known placebo response rate ( $<10\%$ ), with response defined as 50% change in SALT score (50% regrowth) from baseline, at weeks 12, 36 and 48.
3. Comparison of the proportion of subjects in the experimental group and the proportion of subjects in the historical control group attaining global overall improvement SALT score of A5 (100% coverage) supported by  $\leq$  SALT 25 at weeks 12, 24, 36 and 48.
4. Change in PGA (Physician Global Assessment) based on evaluation of live evaluations and standardized photographs between baseline, week 12, 24, 36 and 48.
5. Change in patient global assessment between baseline, Week 12, 24, 36 and 48.
6. Change in patient quality of life assessment from baseline to weeks 12, 24, 36 and 48.
7. Frequency of occurrence and timing of relapse (as defined above) in responders followed for 6 months off therapy.
8. Safety will be evaluated as a secondary endpoint using descriptive statistics to summarize the cumulative incidence and types of AEs.
9. The proportion of patients who discontinued treatment will be summarized.

[figure not shown]

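### Sections 6.4.2 and 7.3 treat weeks 36 and 48 as post-treatment, but for subjects given the optional extension those weeks can be on-drug visits or have no scheduled visit

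*Combined protocol and SAP*

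**What the plan says.** Section 7.3 item 2 takes percent regrowth "determined by SALT measurements following 12, 24 weeks of treatment and at weeks 36 and 48 following discontinuation of treatment". Item 1 of the detailed list in 6.4.2 has the same outcome "following 12, 24 weeks of treatment and during the observational phase at weeks 36 and 48". The responder comparison in 7.3 item 3 is made "with response defined as 50% change in SALT score (50% regrowth) from baseline, at weeks 12, 36 and 48". Like 7.3 items 4 to 7 and 6.4.2 items 2 to 6, it names calendar weeks and is silent on whether the subject is still on drug.

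The Synopsis, 4.1 and 6.4.1 allow an extension; in 6.4.1's words, "Treatment may be extended by up to an additional 6 months beyond the initial 6 months of treatment". Section 4.1 gives extended subjects their own visit track: "every 6 weeks after week 24 while on the study medication, then at 12 weeks and 24 weeks after completion". Section 6.1 lists extension visits under "Weeks 30, 36, 42, 48 (Extension Option"), and Table 3 has a matching optional column. The Table 3 row "Patient observed self-administering study medication" is marked in that column and blank in both post-treatment columns.

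Section 2.2 items 1 and 2 are tied to the end of treatment and the six months after it. Items 3, 4, 7 and 8 of 2.2 keep calendar weeks and add later ones. Section 7.4.3 plans descriptive summaries and does not mention the extension.

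On who is followed after week 24, 4.1 has nonresponders continuing, to look for a delayed response. Section 6.4.2 does not require them to take part, but does follow partial responders.

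**The concern.** Section 4.1 gives the purpose of the week-36 and week-48 visits: to see whether a response lasts, or appears late, once drug has stopped. That reading needs everyone in the summary to be off drug, for a known time. The extension breaks this condition, and the endpoint lists do not allow for it. A week-48 proportion could combine subjects 24 weeks off drug with subjects still on treatment. Because the extension is given on clinical grounds at the investigator's discretion, extended subjects are also a selected group. Section 7.4.3 says these summaries should help design later trials, so their meaning matters even though they are descriptive.

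**Working it through.** **The plan's own figure.** The documents give no number for this point. The only design figure is the 80.7% power in 7.1 (15 subjects, 10% against 40%, alpha 5%). A two-sided arcsine approximation comes close: Φ[(2·arcsin√0.40 − 2·arcsin√0.10)·√15 − 1.96] = Φ(0.851) = 80.3%. That figure concerns the week-24 comparison and does not enter what follows.

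**Inputs.**
- Treatment ends at week E, from 24 to 48 (Synopsis and 4.1: up to 24 extra weeks).
- Visits while on the extension fall at weeks 30, 36, 42 and 48, up to E (4.1, 6.1, Table 3).
- Post-treatment visits fall at E + 12 and E + 24 (4.1, 6.1, Table 3).
- Extensions shorter than 24 weeks are foreseen. The post-extension observation period in 6.1 starts at week 40, and 40 − 12 = 28.

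**Visit map.**

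| E | On-drug visits after week 24 | E + 12, E + 24 | Week 36 | Week 48 |
|---|---|---|---|---|
| 24 (no extension) | none | 36, 48 | 12 weeks off | 24 weeks off |
| 30 | 30 | 42, 54 | no visit | no visit |
| 36 | 30, 36 | 48, 60 | on drug / end of treatment | 12 weeks off |
| 42 | 30, 36, 42 | 54, 66 | on drug | no visit |
| 48 | 30, 36, 42, 48 | 60, 72 | on drug | on drug / end of treatment |

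**All 24 whole-week extension ends, E = 25 to 48, by nominal week.**
- Week 36 is an on-drug or end-of-treatment visit when E ≥ 36, which is 13 cases. It is an off-drug visit only if E + 12 = 36 or E + 24 = 36, that is E = 24 or 12, so in 0 cases. It has no visit in 24 − 13 = 11.
- Week 48 is an on-drug or end-of-treatment visit when E = 48, which is 1 case. It is an off-drug visit when E + 12 = 48, that is E = 36, also 1 case. It has no visit in 24 − 2 = 22.

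These are counts of possible schedules, not of subjects; the documents do not say how often each would occur.

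**Visit windows.** With ±7 days, weeks 36 and 48 cover 35–37 and 47–49. For E = 30 the post-treatment visits cover 41–43 and 53–55; for E = 42 they cover 53–55 and 65–67. None overlaps. A post-treatment window can touch week 36 or 48 only when treatment stops within two weeks of week 24 or week 36, so the windows soften the edges without removing the problem.

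**Does the result depend on partial extensions?** The missing visits do. The label does not: if every extension ran the full 24 weeks, both weeks would be on-drug or end-of-treatment visits, and the post-treatment label would be wrong at both.

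**The case against.** The strongest answer is that the protocol does distinguish the two states. Section 2.2 items 1 and 2 name end of treatment and the period after it separately. The relapse outcome, 7.3 item 8, is confined to responders off therapy. Table 3 puts extension visits and post-treatment visits in different columns, and 4.1 assigns durability and delayed effect in extended subjects to the visits 12 and 24 weeks after completion. All of this stands. A reader might infer that nothing in the plan separates on-drug from off-drug values, or that durability cannot be assessed at all; the documents support neither. What they lack is the separation in the week-36 and week-48 items of 6.4.2 and 7.3, and in 7.4.3. A visit track says when subjects are seen, not how their values are summarised.

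Nor does any section state that on-drug and off-drug values will be pooled; the mixing follows from applying the calendar-week definitions literally. Only 7.3 item 2 and 6.4.2 item 1 carry the wrong label; the other items are ambiguous.

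The statement in 4.1 that all patients are seen at weeks 36 and 48 might be read as adding visits for extended subjects. It sits under an off-medication heading and is followed by the separate extension track, so two tracks is the better reading.

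On nonresponders, a reader might infer that a delayed effect could not be seen. That goes too far: 6.4.2 makes attendance optional rather than barring it, and keeps partial responders in follow-up. It might also be tempting to size the conflict by setting all 15 subjects against week-24 responders alone, but 6.4.2 sets no such denominator.

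Finally, this is a 15-subject open-label pilot with descriptive secondary outcomes. That limits the weight of the point but does not make the summaries interpretable.

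**Conclusion.** The point holds in this limited form. The post-treatment label in 7.3 item 2 and 6.4.2 item 1 is wrong for extended subjects, apart from week 48 when treatment stops at week 36, and the other calendar-week items leave treatment status open. Followed as written, the week-36 and week-48 summaries cannot by themselves show durability. The size and direction of the distortion cannot be derived, because the documents give neither an extension rate nor an off-drug response rate. The conclusion assumes that extended subjects follow the 4.1 extension schedule; the no-visit cases further assume that an extension may stop before its full length. The primary endpoint at week 24 and the 80.7% power are untouched. The contradiction between 4.1 and 6.4.2 on nonresponder follow-up is separate and real, and leaves the denominator of every post-week-24 proportion unsettled. The changes should be made, but this is not a flaw in the main result.

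**What to change.** Carry the end-of-treatment anchor of 2.2 items 1 and 2 into 6.4.2 and 7.3. Define the off-drug outcomes at the existing visits 12 and 24 weeks after end of treatment, and summarise them separately for subjects with and without the extension. If calendar weeks 36 and 48 are kept, report them by treatment status at the visit, with the number of subjects who had no scheduled visit. Put the same rule in 7.4.3.

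Separately, reconcile 4.1 with 6.4.2 on follow-up of nonresponders and partial responders, and state the denominator of each proportion after week 24.

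Re-anchoring needs no new visits. Its cost is small groups. If, for illustration, 5 of 15 subjects were extended, 2/5 has an exact (Clopper-Pearson) 95% interval of 5.3% to 85.3%, and 1/10 one of 0.3% to 44.5%. Reconciling 4.1 with 6.4.2 is more than wording, since it may change which nonresponders attend follow-up.
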